#### **Secondary Objectives:**

To compare the following surgical and clinical outcomes between the two study groups

- To compare correction of alignment after total knee replacement via long standing AP hip-knee-ankle x-rays.
- To compare the accuracy of tibial slope angle on a lateral knee x-ray
- To compare the number of trays sent to sterilization
- To compare the volume of estimated blood loss during the procedure
- To compare the drop in post-operative (day 1) hemoglobin and total volume of transfusions (allogeneic and/or autologous)
- To compare the occurrence of adverse events
- To compare the waste weight at the end of each surgery, considering separately those recyclable and those not recyclable.
- To compare the rate of intraoperative and post-operative complications
- To compare the rate of successful use of MyKnee® cutting blocks (i.e. the incidence of surgical cases where the surgeon did not need to abort the use of MyKnee intra-operatively and default to the use of standard cutting blocks).

The cost-per-minute value based on hospital estimates will be used to calculate an overall cost-savings total.

## 2

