#### **4.1 Data Analysis**

The objectives of this study are outlined in Section 1.3. For purposes of this study, economic outcomes of interest include the peri-operative time, intra-operative time (OR efficiency), and sterilization times as quantitative values. These outcomes will be subsequently used in comparative cost analyses. The secondary objectives are to assess the accuracy of mechanical axis alignment and posterior tibial slope after total knee replacement, additional operative parameters, and adverse events.

Descriptive statistics, specifically means will be used to summarize the peri-operative, intra-operative and sterilization time data.

The primary objective will be met by comparing mean values of each of the time-saving parameters. The null hypotheses of no differences in mean values between re-usable and single-use devices will be tested using separate t-tests for two independent groups for each endpoint. A p-value of less than 0.05 will be considered significant for each endpoint. Endpoints with statistically significant differences are expected to contribute to expected cost differences to be determined in subsequent analyses.

Descriptive analyses as well as similar two-sample comparisons will be used to evaluate secondary measures.

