#### **4.2 Sample Size Analysis**

Sample size for this study was determined on the basis of device group differences observed in the Mont et al 2013 study for four (related) but important health care utilization endpoints. The table below summarizes the data in Table 2 of Mont et al, but also provides a summary of the comparisons between single-use and re-usable pooling over whether or not navigation was employed. These data were used to approximate the expected effect size (standardized mean difference) comparing between single-use vs re-useable instruments. The sample sizes required for a two sample t-test to obtain 80%, 85%, and 90% power as a function of the observed pooled effect sizes were determined. The effect sizes were derived from the reported mean differences and p-values. The maximum sample size per group required to achieve at least 80% statistical power to reject the null hypothesis of equal group mean was determined across the four outcomes summarized in Table 2. For the 2:1 allocation between the single-use Efficiency instruments with MyKnee versus traditional metal instruments, this sample size was 200:100 or total N=300. This value was increased by 14% to N=342 to account for uncertainty in the estimated effect sizes, to account and to allow for additional analyses of economic outcomes. Therefore, 228 and 114 patients will be randomly allocated into single-use Efficiency instruments and traditional metal instruments arms respectively.

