### Sample Size Analysis for Main Effect of Traditional vs Single-Use Devices

Outcome	Instrument	Traditional		Single-Use		Mean Difference (d)	p-value	SD from means and p-value	Analysis			
		Nevi.	patients	Mean	patients				Effect Size = d/SD	N total 2:1 (80%)	N total 2:1 (85%)	N total 2:1 (90%)
Instrument Set-up Time	No	96	36.61	95	33.56	3.050	0.002	6.82	0.447	300	340	400
	Yes	97	39.00	100	35.96	3.040	0.042	10.49	0.290			
	Comb.	193	37.42	195	34.43	2.985		8.66	0.345			
Instrument Cleanup	No	96	16.43	95	13.59	2.840	0.001	5.96	0.476	240	275	320
	Yes	97	24.96	100	20.09	4.870	0.011	13.44	0.362			
	Comb.	193	20.50	195	16.75	3.752		9.72	0.386			
Combined	No	96	53.04	95	47.15	5.890	0.001	12.37	0.476	180	195	225
	Yes	97	63.96	100	56.05	7.910	0.001	16.87	0.469			
	Comb.	193	57.92	195	51.18	6.737		14.63	0.460			
Surgical Episode Time	No	96	100.58	95	97.11	3.470	0.100	14.58	0.238	290	330	385
	Yes	97	128.51	100	119.61	8.900	0.001	18.98	0.469			
	Comb.	193	113.43	195	107.54	5.893		16.79	0.351			

## 5

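### Section 4.1 can be read as letting only time endpoints with p<0.05 into the cost difference; this conflicts with its own unconditional cost statements and, if applied, would bias the total

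*Combined protocol and SAP*

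**What the plan says.** Three statements bear on how time differences become a cost difference.

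- Section 4.1 names the time outcomes as the economic outcomes and adds: "These outcomes will be subsequently used in comparative cost analyses". It attaches no significance condition.
- Later in Section 4.1, the null hypotheses "will be tested using separate t-tests for two independent groups for each endpoint", and "A p-value of less than 0.05 will be considered significant for each endpoint". The next sentence is: "Endpoints with statistically significant differences are expected to contribute to expected cost differences to be determined in subsequent analyses".
- The Secondary Objectives in Section 1.3 end with: "The cost-per-minute value based on hospital estimates will be used to calculate an overall cost-savings total". Again there is no condition.

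Section 3.3 lists 14 timed items: 3 for room preparation and clean-up, 4 intra-operative and 7 for sterilization. Nowhere does the plan define the cost model, say which items are summed, or say what happens to an item whose difference is not significant.

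**The concern.** The sentence on significant endpoints is the only place where the plan links the test results to the costing. If p-values played no part in the costing, it would have little purpose, so an analyst could fairly take it as an inclusion rule. A p-value is a poor rule for that. A real gain or loss that misses 0.05 would leave the total, and one that passes would enter at an estimate that selection has pushed away from zero.

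The sample size table shows how arbitrary the result can be. In its non-navigated rows, "Surgical Episode Time" differs by 3.47 min with p=0.100 and would drop out, while set-up time differs by a smaller 3.05 min with p=0.002 and would count.

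Section 1.3 offers these results to surgeons, facilities and payors who choose instrumentation. With two incompatible rules in the text and 14 items, the choice of components could also be made after the p-values are known. The problem is distinct from multiplicity and from overlapping times: it would remain with a corrected alpha and with components that do not overlap.

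**Working it through.** **Inputs.** Differences d and SDs come from the table in Section 4.2, and arm sizes 228 and 114 from the text of Section 4.2. Alpha is taken as two-sided 0.05. The estimates are treated as normal and the components as independent.

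**The plan's own figure.** Section 4.2 bases N on "The maximum sample size per group required to achieve at least 80% statistical power to reject the null hypothesis of equal group mean". Set-up time, with effect size 0.345, is the binding endpoint. Control arm n = 1.5 × (1.960 + 0.842)² / 0.345² ≈ 99, total 297; the exact t version gives 300. Then 300 × 1.14 = 342. The stated figures reproduce, and nothing below alters them.

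**The filter.** SE = SD × √(1/114 + 1/228) = SD × 0.1147. A component is credited with its estimate if the estimate exceeds c = 1.96 × SE in absolute value, and otherwise with 0. Put a = (c − d)/SE and b = (−c − d)/SE. Then:

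- P(significant) = 1 − Φ(a) + Φ(b)
- mean credited = d × P + SE × [φ(a) − φ(b)]
- mean when significant = mean credited / P

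**Pooled rows, the effects on which the trial was sized.**

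| Component | d | SD | SE | P | Mean when significant | Mean credited |
|---|---|---|---|---|---|---|
| Set-up | 2.985 | 8.66 | 0.993 | 85% | 3.25 (+9%) | 2.77 (−7%) |
| Clean-up | 3.752 | 9.72 | 1.115 | 92% | 3.93 (+5%) | 3.62 (−4%) |
| Episode | 5.893 | 16.79 | 1.926 | 86% | 6.38 (+8%) | 5.51 (−6%) |

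True sum 2.985 + 3.752 + 5.893 = 12.63 min. Credited sum 2.77 + 3.62 + 5.51 = 11.90 min, a ratio of 0.942, about 6% low. The table's Combined row is left out because it already adds set-up and clean-up (36.61 + 16.43 = 53.04 in the non-navigated traditional group). The sum is illustrative, since the plan does not say which components will be added.

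**Non-navigated rows.** Episode time: SE = 14.58 × 0.1147 = 1.672, c = 3.278, a = −0.115, b = −4.035, so P = 0.546. Mean credited = 3.47 × 0.546 + 1.672 × 0.396 = 2.56 min (−26%). Mean when significant = 2.56 / 0.546 ≈ 4.68 min (+35%). Set-up (3.05, SD 6.82) and clean-up (2.84, SD 5.96) are significant in 97% and 99% of trials and are credited on average with 3.02 and 2.82 min. True sum 3.05 + 2.84 + 3.47 = 9.36 min; credited 3.02 + 2.82 + 2.56 = 8.40 min, about 10% low.

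**Mixed directions.** Assume, as no document states, that Group A is truly 2 min slower on episode time, and keep the other two non-navigated rows. Then a = 3.156, b = −0.764 and P = 0.223, so the loss is dropped in 78% of trials. Its mean credited value is −0.94 min instead of −2. True sum 3.05 + 2.84 − 2 = 3.89 min; credited 3.02 + 2.82 − 0.94 = 4.90 min, or +26%.

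**Smaller effects.** At an assumed effect size of 0.20, P is 41%, the estimate is 54% too high when significant, and the mean credited value is 36% low.

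**The case against.** The strongest reply is that the plan states no filter. The sentence voices an expectation about later work. It does not say that significant endpoints alone count, and no section sets a non-significant difference to zero. The two other statements on costing carry no condition. This stands: a reader might infer that exclusion is the plan's declared rule, but the documents do not go that far. What they contain is a sentence that invites that rule beside statements that contradict it, with nothing to settle the matter.

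A second reply is that the bias is small where the trial is planned to operate, and that it shrinks the apparent saving when all effects favour one arm. This also stands. A reader might infer that the filter must exaggerate savings, but on both sets of table rows the average total is too low. An excess needs effects in opposite directions, and the 2-minute loss used to show it is an assumption. A figure of +50% (5.84 against 3.89 min) would describe only the 78% of trials in which that loss is dropped; the average over all trials is +26%.

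The choice of rows can be argued either way. The trial was sized on the pooled effects, but neither arm is described as navigated, so both sets are shown.

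Finally, the cost comparison is a derived step. The t-tests that serve the primary objective and the sample size are untouched.

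**Conclusion.** The point holds as a conflict in the plan that should be fixed; it is not a proven error in a declared cost formula. Section 4.1 can naturally be read as a p<0.05 filter on cost components, and that reading contradicts both the same section and Section 1.3.

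If the filter were applied, the total would be biased by about −6% at the pooled planning effects and about −10% with the non-navigated rows, and by +26% in the assumed mixed case. An ordinary confidence interval around it would ignore the selection and so would not be valid. If all components enter regardless, each difference of means is unbiased and this problem does not arise.

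The sizes rest on the table's differences and SDs being true, 228:114 analysed, normal estimates and an illustrative three-component sum. Independence was assumed, but the average totals do not depend on it, because means add whatever the correlation.

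**What to change.** Delete the sentence in Section 4.1 that ties significant endpoints to the cost difference. Replace it with wording such as: *The cost difference is computed from one pre-specified, non-overlapping set of time components for every patient, whatever the p-value of any component. Components are costed and summed within patient, and the arm means of the per-patient total are compared with a 95% confidence interval (unequal-variance or bootstrap).* List the components by their Section 3.3 labels. Keep the separate t-tests of the time parameters as planned.

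The cost is SAP wording and one per-patient sum, with no new data and no change to N. The interval will be wider than one computed from significant components alone, because the non-significant components add noise. That width is a fair statement of what the trial knows about the total.

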#### **4.2 Sample Size Analysis**

Sample size for this study was determined on the basis of device group differences observed in the Mont et al 2013 study for four (related) but important health care utilization endpoints. The table below summarizes the data in Table 2 of Mont et al, but also provides a summary of the comparisons between single-use and re-usable pooling over whether or not navigation was employed. These data were used to approximate the expected effect size (standardized mean difference) comparing between single-use vs re-useable instruments. The sample sizes required for a two sample t-test to obtain 80%, 85%, and 90% power as a function of the observed pooled effect sizes were determined. The effect sizes were derived from the reported mean differences and p-values. The maximum sample size per group required to achieve at least 80% statistical power to reject the null hypothesis of equal group mean was determined across the four outcomes summarized in Table 2. For the 2:1 allocation between the single-use Efficiency instruments with MyKnee versus traditional metal instruments, this sample size was 200:100 or total N=300. This value was increased by 14% to N=342 to account for uncertainty in the estimated effect sizes, to account and to allow for additional analyses of economic outcomes. Therefore, 228 and 114 patients will be randomly allocated into single-use Efficiency instruments and traditional metal instruments arms respectively.

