### 3.2.2

#### **Randomization**

Patients will be randomized using a computer generated blocked randomization with 2:1 allocations to the single-use Efficiency instruments (and MyKnee) versus traditional metal instruments (conventional TKA) groups. The randomization will be performed separately for each site.

In case the investigator decides not to include the patient after randomization, this patient will be treated as withdrawn although a randomization has been performed. The reason for withdrawal must be documented in the patient file. The used randomization number cannot be used again. For the next patient, the following randomization number will be used.

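### Section 4.2's single statement of at least 80% power rests on SDs and differences pooled over navigation that match neither a mixed nor a non-navigated trial; power for surgical episode time should be restated as a range

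*Combined protocol and SAP*

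**What the plan says.** Section 4.2 takes its effect sizes from a published comparison of instrument types, using a summary of "single-use and re-usable pooling over whether or not navigation was employed". Sample sizes are then found "as a function of the observed pooled effect sizes", and the largest of the four is adopted: "The maximum sample size per group required to achieve at least 80% statistical power to reject the null hypothesis of equal group mean". That is 200:100, or 300 in total. The plan adds: "This value was increased by 14% to N=342 to account for uncertainty in the estimated effect sizes".

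The table under Section 4.2 has non-navigated, navigated and combined rows for four outcomes: instrument set-up, instrument clean-up, their sum, and "Surgical Episode Time".

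Section 4.1 tests the time parameters with "separate t-tests for two independent groups for each endpoint", each at 0.05, with no covariate. Navigation appears only in the sample-size section and its table and in a cited title. It is not in the eligibility criteria, the descriptions of Groups A and B, the randomization or the analysis.

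**The concern.** A power calculation should use the SD and the difference that the planned test will meet. The combined rows draw on two settings whose mean surgical episode times are 22 to 28 minutes apart, yet the combined SD is barely above the average of the two within-setting SDs. An unadjusted t-test on mixed cases would carry that gap as extra variance. If all cases are non-navigated, the SD is smaller than the pooled one, but the table's difference for that setting is smaller too.

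Intra-operative time is named in the primary objective (Section 1.3). A reader who takes the 80% at face value could read a non-significant intra-operative result as better evidence of no saving than it is.

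**Working it through.** **Method.** Two-sided two-sample t-test at 0.05, 2:1 allocation, noncentral t with df = N - 2 and noncentrality (d/SD)/√(1/n1 + 1/n2). The root is 0.1225 at 200:100 and 0.1147 at 228:114. Differences, SDs and means come from the table under Section 4.2.

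**1. The plan's own figure.** Set-up, combined row: 2.985/8.66 = 0.345, and 0.345/0.1225 = 2.82, which gives 80% power at N=300. It reproduces. Surgical episode: 5.893/16.79 = 0.351, N = 291 (stated 290). Clean-up: 240 (stated 240). The sum of the two gives 168-171 against a stated 180, which does not affect the maximum.

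**2. What the combined SDs are.** Plain averages of the two within-setting SDs:

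| Outcome | Average of the two SDs | Combined SD stated |
|---|---|---|
| Set-up | (6.82 + 10.49)/2 = 8.655 | 8.66 |
| Clean-up | (5.96 + 13.44)/2 = 9.70 | 9.72 |
| Sum of the two | (12.37 + 16.87)/2 = 14.62 | 14.63 |
| Surgical episode | (14.58 + 18.98)/2 = 16.78 | 16.79 |

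The gap between settings is therefore left out. For surgical episode time it is 128.51 - 100.58 = 27.93 min (traditional) and 119.61 - 97.11 = 22.50 min (single-use).

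**3. Mixed settings, 50:50, surgical episode time.**
- Difference: (3.47 + 8.90)/2 = 6.185 min.
- Within-setting variance: (14.58² + 18.98²)/2 = 286.4 (SD 16.92).
- Total variance: 286.4 + 0.25 × 27.93² = 481.4 (traditional) and 286.4 + 0.25 × 22.50² = 413.0 (single-use). Weighted 1:2 this is 435.8 (SD 20.88).
- Effect size: 6.185/20.88 = 0.296.

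| Assumption at 50:50 | N=300 | N=342 |
|---|---|---|
| By-setting differences, navigation random between arms | 67% | 73% |
| By-setting differences, navigation fixed by site | 71% | 78% |
| Pooled 5.893 min (5.893/20.88 = 0.282), navigation random between arms | 63% | 69% |

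The second row applies if each site uses one method throughout, because "The randomization will be performed separately for each site" and navigation is then balanced between arms. The arm difference varies with SD 16.92, while the t-test still uses 20.88.

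Repeating this for every share of navigated cases, with by-setting differences, the best attainable lowest power among the four outcomes at N=300 is 75% (77% if fixed by site). At N=342 all four reach 80% only at about 61-65% navigated (54-66% if fixed by site).

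**4. No navigation, surgical episode time, SD 14.58.**

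| Assumed difference | Effect size | N=300 | N=342 |
|---|---|---|---|
| 3.47 min (non-navigated row) | 0.238 | 49% | 54% |
| 4.7 min | 0.322 | 75% | 80% |
| 5.893 min (combined row) | 0.404 | 91% | 94% |

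The other three outcomes, on their non-navigated rows, have 97% (set-up) and 98-99% (clean-up, sum) at N=342. Here the SD is not the problem: it is below the pooled 16.79, and the fall to 54% comes wholly from the smaller difference.

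**5. How firm the 3.47 minutes is.** SE = 14.58 × √(1/96 + 1/95) = 2.11, so the 95% CI is about -0.7 to 7.6 min, which contains 5.89. The navigated SE is 18.98 × √(1/97 + 1/100) = 2.70. The two differences are 8.90 - 3.47 = 5.43 min apart, with SE √(2.11² + 2.70²) = 3.43, so z = 1.58 and p is about 0.11.

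**The case against.** The strongest defence is that pooling is disclosed, N=300 reproduces, and a within-setting SD is a normal choice for a main effect. The rows do not establish that the saving depends on navigation (p about 0.11). If the pooled 5.893 minutes holds without navigation, power is above the plan's claim. Group A also adds patient-matched blocks, for which Section 1.2 claims a reduction in resection steps and related time, so the saving may be larger than in the cited study. N was raised partly for effect-size uncertainty. All of this stands, and it rules out calling the calculation an arithmetic error or putting 54% forward as the finding. It does not rescue the single 80% figure: a within-setting SD suits an analysis that adjusts for setting, and Section 4.1 plans none.

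A reader might also infer that a real saving which misses significance would drop out of the cost comparison, because "Endpoints with statistically significant differences are expected to contribute to expected cost differences to be determined in subsequent analyses". The documents do not support that. The same section says earlier, with no significance condition, that the time outcomes will be used in the cost analyses, and Section 1.3 applies a cost per minute without one.

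Finally, surgical episode time is not among the intra-operative times listed in Section 3.3. It is a proxy for them, and the documents give no mapping.

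**Conclusion.** Wrong as written; minor severity. The 80% statement follows from its inputs, but those inputs describe neither a mixed nor a non-navigated trial. With mixed settings and the planned unadjusted tests, surgical episode power at 50:50 is 63-71% at N=300 and 69-78% at N=342, depending on the difference assumed and on whether navigation is fixed by site. Without navigation, power at N=342 runs from 54% to 94% over differences of 3.47 to 5.89 minutes, and the other three outcomes are comfortably powered.

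The tempting stronger reading is that the trial has only 54% power for intra-operative time. That would need three things the documents do not give: confirmation that navigation is not used (it is inferred from the descriptions of Groups A and B), evidence that the true difference is 3.47 minutes, and a link from surgical episode time to the Section 3.3 measures.

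The by-setting inputs are imprecise (95-100 patients per arm) and treat the table's rounded p-values as exact. A navigated p of 0.0005-0.0015 would put that SD at about 17.9-19.7. These are planning values.

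**What to change.** Keep N=342.

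1. In Section 4.2, state whether navigation will be used, and replace the single 80% statement with power for that setting over a range of surgical-time differences. For no navigation, for example: *At N=342 (228:114), power is about 97% for set-up time and 98-99% for clean-up and combined time. For surgical episode time (SD 14.58) it is about 54% at a difference of 3.47 min, 80% at 4.7 min and 94% at 5.9 min. These figures rest on imprecise subgroup estimates (95-96 patients per arm).*

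2. Only if settings are mixed, record planned navigation before randomization and adjust the time comparisons for it. At 50:50 and N=342, using the within-setting SD, this gives about 85% for set-up (3.045/8.85) and 89% for surgical episode time (6.185/16.92).

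Item 1 costs two or three sentences and leaves the planned tests unchanged; its downside is a less favourable stated power for surgical episode time. Item 2, if it applies, adds one data field and an adjusted comparison in Section 4.1.
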